**Figure 1. Schematic Diagram of Study Design**

Noninvasive transthoracic echocardiograms will be performed to assess RV function before and after the 12-week study treatment period. The first 10 subjects enrolled will receive the first dose of the study drug in the cardiac catheterization laboratory to evaluate acute pharmacological responses during the screening RHC (Visit1). This will be repeated at the end of the 12-week study RHC (Visit 7). Hemodynamic measures such as pulmonary vascular resistance (PVR), mean pulmonary artery pressure (mPAP) and left and right ventricular filling pressures, will be measured at baseline and 30 minutes post drug dose and CXA 10 metabolites will be measured with pharmacokinetics sampling time points at baseline and 2-6 hours post drug as outlined in PK sampling window table in Section 2.2.3.. Food will be given prior to dosing.

Subjects will have 6-minute walk distance with Borg dyspnea scale assessments during the screening visits. Plasma N-terminal pro-brain natriuretic peptide (NT-proBNP) level, the World Health Organization (WHO) Functional Class assessment, and health related quality of life questionnaire will also be collected.

Subject will continue the oral CXA-10 300 mg once daily in the morning with food at home for 12 weeks. Throughout the outpatient study treatment period, subjects will be asked to remain diligent in recording the exact date and time of CXA-10 dosing with any associated symptoms. Subjects will be evaluated at 4-week intervals for occurrences of adverse events, laboratory test abnormalities, and evaluations of NT-proBNP plasma levels, six-minute walk distance with Borg dyspnea scale assessments, and WHO functional classification and health related quality of life questionnaire recorded. Additional blood samples will be obtained for biomarkers and cytokines analysis before and after study drug treatment. An IVGTT will be performed before and after 12 weeks of CXA-10 treatment to measure insulin secretion and sensitivity.

To quantify physical activities, a noninvasive accelerometer will be used for physical activity monitoring. The device must be worn for a minimum of 7 days at home prior to receiving the first dose of CXA-10 and prior to the end of study drug treatment visit (Week 12). Measurements will include sleep and wake activity over the entire 24-hour period each day it is worn.

After 12 weeks of study treatment, subjects will return for a repeat right heart catheterization, in addition to all study endpoints. PK samples and plasma NT-proBNP will be collected. All subjects, regardless of whether they completed study treatment or discontinued study treatment prematurely, will be asked to return for a safety follow-up visit (4 weeks after stop of study medication intake). Additional follow-up assessments by telephone will occur in between each outpatient clinic visit at Weeks 2, 6 and 10.

Throughout the study, subjects will be monitored carefully for occurrences of adverse events, laboratory test abnormalities, and changes in vital signs. The expected duration of each subject's participation in this proposed clinical investigation is approximately 5 months.

## **2.2.2 Study Visits and Assessments**

Outlined below are study procedures that will be performed at screening, during the study treatments, and at follow-up. See Appendix A for the complete study assessment and procedures.

### **Visit 1 (Screening)**

Screening assessment will be performed within about 4 weeks prior to baseline testing (Visit 2) and will take place on two (2) separate days if a screening right heart catheterization (RHC) is needed. Subjects will be asked to fast a minimum of 8 hours prior to each visit.

- Obtain written informed consent.
- Review Inclusion and Exclusion criteria
- Medical history review and demographics
- Complete physical exam
- Weight, height
- Electrocardiogram (ECG)
- Vital signs (temperature, respiratory rate, blood pressure, heart rate) and pulse oximetry
- Clinical lab testing and urinalysis (fasting glucose, comprehensive metabolic panel, fasting lipid profile, complete blood count, platelet and differential [CBC/Diff/Plt], uric acid, PT/INR and hemoglobin A1C).
- RHC. This will be completed if not done within the prior 2 months to verify eligibility or may be repeated at study PI discretion. For a RHC to be considered eligible within 2 months, the subject must be stable on their medications and should not have started a new exercise program right before the prior cath or since the RHC within 2 months leading up to screening or baseline. Pulse oximetry and automated blood pressures will be measured at regular intervals.
- Hemodynamic measures such as pulmonary vascular resistance (PVR), mean pulmonary artery pressure (mPAP) and left and right ventricular filling pressures, will be measured at baseline and 30 minutes post drug dose and CXA 10 metabolites will be measured with pharmacokinetics sampling time points at baseline and 2-4 hours post drug dose. Food will be given prior to dosing. Research blood samples for biomarkers, cytokines measurements (samples collected at the same times as PK samples)
- NT Pro-BNP
- Urine pregnancy test in women of childbearing potential (i.e. women who are not at least 1 year post-menopausal or who have not undergone a surgical sterilization procedure)
- Pulmonary function testing (PFT) must have been completed, no more than 12 months prior to the start of screening visit. If this has not been performed, a new PFT will be obtained.
- 6 minute walk test (6MWT) with Borg Dyspnea Scale
- Oral (saliva, tongue scraping) and stool samples for microbiome analysis; subjects may be provided a stool collection kit and return the sample in a pre-paid envelope by USPS mail.
- WHO Functional Class assessment
- Concomitant medications assessment
- AE assessment
- Attach accelerometer to the subject's non-dominant wrist after all assessments have been completed and all eligibility criteria are met. The device must be worn for at least 7 consecutive days prior to receiving the first dose of study medication in order to collect baseline activity. Subjects will be instructed to return the accelerometer at the next visit.

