#### Visit 2 (Week 0- Baseline testing)

This visit will take place at UPMC Montefiore. Subjects will be asked to fast a minimum of 12 hours to perform the assessments listed below.

- Brief physical exam with a body weight measurement and WHO Functional class assessment
- Vital signs (temperature, blood pressure, respiratory rate, heart rate, and pulse oximetry measurements are taken).
- ECG
- Echocardiogram (this test may be completed at any visit prior to first dose of drug)

- Clinical laboratory tests and urinalysis (fasting glucose, comprehensive metabolic panel, fasting lipid profile, CBC/Diff/Plt, uric acid, PT/INR)
- Research blood samples for biomarkers, cytokines measurements NT-proBNP
- Urine pregnancy test for female child-bearing potential
- IVGTT
- Health related quality of life questionnaire - Pulmonary Arterial Hypertension-Symptoms and Impact (PAH-SYMPACT®)
- Return accelerometer for data download
- Concomitant medications assessment
- AE assessment

Visit 3 (Week 0 – First dose)

This visit will take place at UPMC Montefiore. Subjects do not need to fast for this visit and this visit will last up to about 4 hours.

- 6MWT
- Blood draw for Population PK sampling (pre-dose and 2-4 hours after taking the study drug)
- Research blood samples for biomarkers, cytokines measurements (samples collected at the same times as PK samples)
- Subjects will be instructed to take the first dose of study medication at the clinic after a breakfast/morning snack containing up to approximately 30% fat
- Dispense study drugs
- Concomitant medications assessment
- AE assessment

Visit 3a (Week 1: +3d)

This visit will take place at UPMC Montefiore or UPMC Presbyterian. This visit will last approximately 30 minutes. Subjects who are on warfarin will be asked to return to the clinic one week after taking the study drug for a blood draw for PT/INR. If the INR value is > 2.5, the warfarin dose may be adjusted per the standard of care. Subjects do not need to fast for this visit.

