
**END OF TREATMENT: All end of treatment study procedures will take place over 3 visits and can be completed in any order to accommodate scheduling needs.**

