**Physical Activity:** Continuous physical activity monitoring will be conducted using a noninvasive accelerometer (Actigraph, Pensacola, FL). All subjects will be instructed to use a noninvasive accelerometer at home during waking hours to quantify physical activities for 8 days to achieve a full 7 wear days, and to take it off only when showering. Measurements will include sleep and wake activity over the entire 24-hour period each day it is worn. The device must be worn for a minimum of 7 consecutive days at home prior to: (1) receiving the first dose of study medication (Visit 3 - Week 0) in order to collect baseline activity, and (2) prior to conducting end of study drug treatment assessments at Visit 6 (Week 12). The study staff will remove the accelerometer when the subject returns for Visit 3 and Visit 6. The study staff will download the data, visually screen the raw accelerometer file for spurious data, perform a battery check, and allocate the unit for redeployment.

**N-Terminal Pro-B-Type Natriuretic Peptide (NT-proBNP):** Blood samples for determination of NT-proBNP serum concentrations will be collected at Screening and at 4-week intervals throughout the study.

**WHO Functional Class:** The World Health Organization (WHO) Classification of Functional Status of Patients with PH will be used to classify disease severity in PAH. It places patients in one of four categories based on how much they are limited during physical activity.

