## **2.4 STUDY ENDPOINTS**

Primary Endpoint:

The primary endpoint measures the incidences of treatment-emergent adverse events.

Secondary Endpoints:

The primary efficacy endpoint measures the change from baseline in Pulmonary Vascular Resistance (PVR) assessed by Right Heart Catheterization at 12 weeks.

Other secondary endpoints measure:

- Change from baseline in hemodynamic parameters including Cardiac Output (CO), Cardiac index (CI), mean Pulmonary Artery Pressure (mPAP), Pulmonary Artery Wedge Pressure (PAWP), Mean Right Atrial Pressure (mRAP), and compliance (SV/ (sPAP-dPAP) at 12 weeks
- Change from baseline in RV function including tricuspid annular plane systolic excursion (TAPSE) and tissue Doppler of the lateral tricuspid valve anulus (S') as assessed by echocardiograms at 12 weeks
- Change from baseline in functional exercise capacity by assessing 6 minute walk distance test with Modified Borg Dyspnea Scale at 12 weeks
- Change from baseline in the levels of serum NT-proBNP at 12 weeks
- Change from baseline in WHO Functional Class at 12 weeks
- Change from baseline in patient reported outcomes measured by PAH-SYMPACT® questionnaire at 12 weeks
- Change from baseline in daily physical activity assessed by personalized activity monitor at 12 weeks
- Pharmacokinetic endpoint: CXA-10 parent and metabolites

Exploratory Endpoints:

- Change in insulin sensitivity by intravenous glucose tolerance test at 12 weeks
- Pharmacodynamic endpoint: change from baseline in serum biomarkers, leptin, inflammatory cytokines (IL-17, IL-6, TNF $\alpha$ , MCP-1) and hsCRP at 12 weeks
- Pharmacokinetic - Pharmacodynamic relationship of CXA-10 on relevant efficacy, safety and biomarkers endpoints, if the data allow
- Epidemiological relationships of oral and gut microbiome and PAH

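### Accelerometer wear instructions conflict, and wear timing relative to right heart catheterization is not controlled at either time point

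*Combined protocol and SAP*

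**What the plan says.** **Endpoint.** Section 2.4 lists as secondary: "Change from baseline in daily physical activity assessed by personalized activity monitor at 12 weeks". Aim 3 names home accelerometry. Section 2.5.2 compares Week 12 with baseline by paired t-test, or by signed rank test if the data are not normal. There is no control arm.

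**Baseline timing.** Section 2.2.2, Visit 1: "Attach accelerometer to the subject's non-dominant wrist after all assessments have been completed and all eligibility criteria are met". It continues: "The device must be worn for at least 7 consecutive days prior to receiving the first dose of study medication". The RHC is one of the Visit 1 assessments and decides eligibility. It is done only if there was none in the previous 2 months, or at the investigator's discretion. Screening then takes two separate days, within about 4 weeks before Visit 2.

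**Week 12 timing.** The device is issued at Week 8 (Visit 5), for at least 7 consecutive days of wear before the Week 12 visit. Section 2.2.3 places this before the Visit 6 assessments. The visit list and Appendix A put the repeat RHC at Visit 7. The note above Visit 6 says that end-of-treatment procedures "can be completed in any order to accommodate scheduling needs".

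**Wear hours.** The Physical Activity paragraph of section 2.2.3 tells subjects to "use a noninvasive accelerometer at home during waking hours", for 8 days so as to obtain 7 full ones, and to remove the device only to shower. It then says: "Measurements will include sleep and wake activity over the entire 24-hour period each day it is worn". Section 2.2.1 also specifies 24-hour measurement.

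**Return.** The Visit 1 text has the baseline device returned at the next visit, the Visit 2 list has "Return accelerometer for data download", and Appendix A agrees with Visit 2. The Physical Activity paragraph says: "The study staff will remove the accelerometer when the subject returns for Visit 3 and Visit 6".

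**First ten subjects.** The synopsis and section 2.2.1 have them take their first dose during the screening RHC.

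**The concern.** A paired comparison without controls attributes to treatment whatever differs between the two measurement weeks. If an invasive procedure can sit next to or inside one week and not the other, and this varies by subject, any short-term effect of the procedure on movement becomes part of the estimated change and cannot be separated afterwards.

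The wear-hours conflict is a separate problem. Some subjects may wear the device only while awake and others around the clock, or one subject may do each at different times. Daily totals then rest on different observation periods, and the intended sleep data are lost for some. Neither section 2.2.3 nor section 2.5.2 defines a valid day or a minimum wear time. The only check described is a visual screen of the raw file for spurious data.

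For the first ten subjects, a device fitted after all Visit 1 assessments goes on after a dose has been given, so it cannot supply the pre-dose baseline that the plan requires.

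**Working it through.** The plan gives no SD, effect size or power for this endpoint, so there is no stated figure to reproduce. The check is a comparison of the texts, followed by an illustration on assumed inputs.

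**1. RHC position, side by side.**

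| | Baseline | Week 12 |
|---|---|---|
| Planned order | RHC (if done), then wear | Wear, then Visit 6, then RHC at Visit 7 |
| Minimum gap to RHC | None stated | None stated |
| Can the order change? | No: fitting follows all assessments | Yes: visits in any order |
| Who is affected | Subjects with a screening RHC; share not given | Subjects whose Visit 7 comes early; share not given |

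If all of the first ten subjects have a screening RHC, as section 2.2.1 implies, the affected share at baseline is at least 10/30, or one third of planned enrolment.

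**2. Illustration for one affected subject.** Let k be the number of affected days out of 7 and r the relative fall in activity on those days. The baseline deficit is b = (k/7) × r, and the apparent gain is b/(1 − b). Neither k nor r is in the documents.

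- k = 0: b = 0, no gain.
- k = 1, r = 0.30: b = 0.30/7 = 4.3%; gain 0.0429/0.9571 = 4.5%.
- k = 2, r = 0.50: b = 1.00/7 = 14.3%; gain 0.1429/0.8571 = 16.7%.

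**3. If the fitting day is also the RHC day and is not analysed.** Eight days of wear for seven full days could mean this. Then k falls by one.

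- The first case becomes zero.
- The second becomes b = 0.50/7 = 7.1%; gain 0.0714/0.9286 = 7.7%.

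**4. Averaged over the cohort.** With a share f affected and similar activity in all subjects, b = f × (k/7) × r. At f = 1/3 and no day dropped:

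- Lower case: b = 4.3%/3 = 1.4%; gain 1.4%.
- Upper case: b = 14.3%/3 = 4.8%; gain 0.0476/0.9524 = 5.0%.

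**5. Opposite sign.** If the RHC falls inside the Week 12 wear week and baseline is unaffected, the same assumptions lower the Week 12 mean by 4.3% to 14.3%, an apparent loss.

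**6. What a net bias would do to the test.** With n = 27 and a two-sided 5% paired t-test, a bias of 0.1, 0.2 or 0.3 SD of the change gives rejection with no drug effect in 7.9%, 17.0% or 32.4% of trials. Without an SD, the percentages in steps 2 to 5 cannot be placed on this scale.

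**7. Wear hours.** Assuming 16 waking hours, waking-only wear omits 8/24, or one third, of the clock day. The omitted hours are mostly sleep, so this is not one third of activity. If a subject follows the same practice in both weeks, no signed bias follows.

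**8. Return visit.** Visits 2 and 3 are both Week 0 and both precede the Visit 3 dose. The conflict affects which days are recorded. It has no evident direction.

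**The case against.** A reader might infer that the activity change is biased toward improvement, because baseline wear comes just after a catheterization and Week 12 wear does not. The documents do not support that, for these reasons.

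- Nothing in them says that activity falls after RHC. Section 6.1 lists site pain, bruising and a slight bleeding risk, and says that sedation should wear off within several hours.
- The screening RHC is conditional, and screening that includes one spans two days, so wear need not start on the day of the procedure.
- Seven days is a minimum, and the plan does not say which seven are analysed. Eight days for seven full ones may already drop the fitting day.
- Free ordering of Visits 6 to 8 allows the opposite error.
- The wear-hours and return-visit conflicts cause noise and non-comparability, without a sign.

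All of this stands, and it removes any claim about direction or size. It can also be said that this is one of many secondary endpoints, with no power calculation or decision rule, and that sleep is not itself a listed endpoint. That too is right, and it limits the importance of the point.

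The objection does not remove the contradictory instructions, the lack of any rule relating wear to RHC, or the conflict over the first ten subjects.

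**Conclusion.** The point holds as a conflict in the instructions and an uncontrolled difference between the two measurement periods. A bias in the activity change is possible, but its direction and size are not established. The 4.5% to 16.7% range is an illustration per affected subject on assumed activity losses. It is not an estimate for the cohort, and it shrinks to zero or reverses under equally permissible readings of the plan.

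The texts do establish that the wear-hours instruction contradicts itself, that the return visit differs between sections, and that no gap from RHC is set at either time point. They also show that the first ten subjects, as described, cannot have pre-dose activity from a device fitted after all Visit 1 assessments. Only the activity endpoint is affected. The primary safety endpoint and the PVR comparison are not. The change is worth making because it is cheap and the endpoint has no control arm to absorb the difference.

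**What to change.** Amend the Visit 1 and Visit 5 instructions in section 2.2.2 and the Physical Activity paragraph of section 2.2.3, and align Appendix A where needed:

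1. Give one wear instruction: 24-hour wear except for showering. Delete the restriction to waking hours.
2. Name one baseline return visit and use it throughout.
3. Apply one rule at both time points: the seven full days analysed exclude any RHC day and a fixed, prespecified number of days after it. The documents give no basis for a particular number, so the sponsor should choose and justify it before data are seen. The screening period of about 4 weeks leaves room.
4. Complete the Week 12 wear block before any of Visits 6 to 8. Their order can then stay flexible.
5. Reconcile the synopsis and section 2.2.1 (first ten subjects dosed at the screening RHC) with the requirement for baseline wear before the first dose, and state how those subjects enter the activity analysis. This point takes no view on when that dose should be given.

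The cost is wording in the protocol and subject instructions, with the same device and visits. The downside is a few more days of wear, or of screening interval, for subjects who have a screening RHC.

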#### Visit 2 (Week 0- Baseline testing)

This visit will take place at UPMC Montefiore. Subjects will be asked to fast a minimum of 12 hours to perform the assessments listed below.

- Brief physical exam with a body weight measurement and WHO Functional class assessment
- Vital signs (temperature, blood pressure, respiratory rate, heart rate, and pulse oximetry measurements are taken).
- ECG
- Echocardiogram (this test may be completed at any visit prior to first dose of drug)

- Clinical laboratory tests and urinalysis (fasting glucose, comprehensive metabolic panel, fasting lipid profile, CBC/Diff/Plt, uric acid, PT/INR)
- Research blood samples for biomarkers, cytokines measurements NT-proBNP
- Urine pregnancy test for female child-bearing potential
- IVGTT
- Health related quality of life questionnaire - Pulmonary Arterial Hypertension-Symptoms and Impact (PAH-SYMPACT®)
- Return accelerometer for data download
- Concomitant medications assessment
- AE assessment

Visit 3 (Week 0 – First dose)

This visit will take place at UPMC Montefiore. Subjects do not need to fast for this visit and this visit will last up to about 4 hours.

- 6MWT
- Blood draw for Population PK sampling (pre-dose and 2-4 hours after taking the study drug)
- Research blood samples for biomarkers, cytokines measurements (samples collected at the same times as PK samples)
- Subjects will be instructed to take the first dose of study medication at the clinic after a breakfast/morning snack containing up to approximately 30% fat
- Dispense study drugs
- Concomitant medications assessment
- AE assessment

Visit 3a (Week 1: +3d)

This visit will take place at UPMC Montefiore or UPMC Presbyterian. This visit will last approximately 30 minutes. Subjects who are on warfarin will be asked to return to the clinic one week after taking the study drug for a blood draw for PT/INR. If the INR value is > 2.5, the warfarin dose may be adjusted per the standard of care. Subjects do not need to fast for this visit.

The rationale for PT/INR measurement in PAH patients on warfarin is that Warfarin is a substrate of CYP2C9. Although the concentrations of CXA-10 *in vivo* are significantly lower than the concentrations *in vitro*, CXA-10 has shown moderate *in vitro* inhibition of CYP2C9. The lowest IC50 value, based on *in vitro* inhibition for CYP2C9, was 2.2  $\mu$ M. The peak plasma concentrations of CXA-10 in humans following oral administration of a 1200 mg dose were less than 10 ng/mL (< 30 nM). Modeling of CXA-10 direct CYP inhibition *in vitro* data for CYP2C9 is projected to yield an R1 value (R1 = 1+[I]/Ki) of 1.02 for CYP2C9, that is less than the R1 value of 1.1, as defined in FDA Guidance Industry February 2012. Therefore, CXA-10 is not expected to increase the exposure to concurrently administered drugs that are primarily cleared by CYP2C9-mediated elimination mechanisms. Even though the potential for a drug-drug interaction is low, we will measure PT/INR on Week 2 for subjects taking warfarin. CXA-10 must reach steady-state concentration before collecting blood for PT and steady state of CXA-10 is achieved by day 7.

Visit 4 (Week 4;  $\pm$  5d) and Visit 5 (Week 8;  $\pm$  5d)

Subjects will report to the clinic on the morning of Week 4 and Week 8 (Visit 4 and Visit 5) after a minimum 8-hour overnight fast. Subjects should not take their study medication that morning, prior to arriving at the clinic for their pre-dose assessment.

- Brief physical exam
- Body weight
- ECG
- Vital signs (temperature, blood pressure, respiratory rate, heart rate, and pulse oximetry measurements are taken).
- Clinical laboratory testing and urinalysis (fasting glucose, comprehensive metabolic panel, fasting lipid profile, CBC/Diff/Plt, uric acid)NT Pro-BNP
- Urine pregnancy test in women of childbearing potential
- 6MWT with Borg Dyspnea Scale
- Health related quality of life questionnaire - PAH-SYMPACT®
- WHO Functional Class assessment
- Dispense study drugs. Subjects will be instructed to take the study medication at the clinic after a breakfast/morning snack containing up to approximately 30% fat
- PK blood sampling (pre-dose and 2-4 hours post-dose)
- Research blood samples for biomarkers, cytokines measurements (samples collected at the same times as PK samples)
- Concomitant medications assessment
- AE assessment
- Provide accelerometer on week 8 only and instruct to wear the accelerometer for at least 7 consecutive days prior to the next visit (Week 12).

**END OF TREATMENT: All end of treatment study procedures will take place over 3 visits and can be completed in any order to accommodate scheduling needs.**

